1.12 MEASURES AND TOOLS

In this study, we will measure three levels of data:

1. Site level data: Characteristics, leadership, readiness, and implementation completion.
2. Clinician level data: Characteristics, attitude toward evidence-based care, efficacy, and training knowledge and completion.
3. Beneficiary level data: Characteristics and outcomes.

We will also examine fidelity to implementation strategies and CAPABLE. Each are described and shown in the Table below.

Characteristic Measures

Characteristics of site, clinician, and beneficiaries will be collected at baseline. Site level data includes size, CQAR scores, number of supervisors/clinicians, number of beneficiaries, and years contracted in waiver.

Clinician level data (RN/OT/SW/IF) includes age, race, gender, discipline, and years working in waiver program site. Beneficiary level data includes age, gender, and race.

Tools

Implementation Leadership Scale (ILS) will be collected at baseline from clinicians to examine organizational leader behavior and actions that actively support implementation of evidence-based practice.⁷⁷⁻⁷⁸ ILS has 12 items with sub-scales (Cronbach's alpha): proactive leadership (.94); knowledgeable leadership (.97); supportive leadership (.93); and perseverant leadership (.94), each with 3-items. Items are scored on a 5-point scale indicating the degree to which a leader performs specific behavior.

Organizational Readiness to Change Assessment (ORCA) will be collected at baseline from clinicians (Cronbach's alpha .88) and used to examine site readiness to implement evidence-based practice.⁷⁹ There are 115 items in the manager tool and 124 in the clinician tool and each has 3-open ended questions regarding readiness. In systematic review of organizational assessments, the TCU-ORC ranked highest for reliability and validity of those available to date.⁷⁹ Scoring for each scale are obtained by summing responses among each scale; then divide by the number of items; and then multiply the mean by 10. Sub-scales include needs (clinician, program, training); pressure for change; resources (offices, clinician, training, equipment, internet, supervision); and attributes (growth, efficacy, influence, adaptability, satisfaction, and orientation).

 3. *Completed all 8 stages*: the completion date is logged in stage 8. For sites that chose to discontinue implementation at any point in the process, the date is logged in the furthest stage that the site enters. In the case where data are summarized before the stage is complete but a site has not discontinued implementation, the site data are treated as being censored, just as it would in a standard time-to-event or survival analysis.⁸³ *Proportion of activities completed* is calculated as the number of activities completed divided by the number of possible activities in each stage. Activities in each stage are ordered based on their logical progression up to the last activity the site completes in the stage or completion of the final activity in the stage.
- Achievement of either activity indicates completion of that stage.

Measures						
DOMAIN	CONSTRUCT	CONCEPT(S)	Aims*	Who Measured	How Measured	Collected by
Inner Setting	Readiness for Implementation	Leadership Engagement	A5	Sites	ILS	PM
		Readiness to implement			ORCA	
		Size of WA Agency			Admin Data 18	
		CQAR Scores			CQAR 2016-18	
Individual: Site and/or person	Demographics	Site # employees/ beneficiary#, CQAR, cost	-	Sites	Admin Data	PM
		Clinician: age/race/ethnicity/sex/discipline/degree/year experience/in WA		Clinician	Survey	
		Age, sex, race, ethnicity, comorbidities		Beneficiary/patient	MDS	
	Clinician: engagement	1. Attitude 2. Self-efficacy	A2	Clinician	1. EBPAS 2. GSE	PM
	Beneficiary/patient outcomes	I/ADLs, falls, pain, depression/ED/hospital	A3 & A4	Beneficiary/patient	MDS	-
Process	Training	Knowledge with CAPABLE	A2	Clinician	Survey	PM
		Knowledge with IF/EF		IF/EF		
	Team Building	Interdisciplinary coordination		Beneficiary/patient	PNs in EHR	-
	Coalition Building	Occurrence/type		IF	Data tool	
Inner Setting	Adoption	Fidelity to training	A1 & A2	Clinician	Type/date/# done	PM
		Fidelity to IF/EF		IF/EF	IF Data tool	RAs
		Fidelity to CAPABLE		Beneficiary/patient	PSCP in EHR	-
	Sustainability	Fidelity to change	A6	Sites	SIC	RAs
	Acceptability	Satisfaction with training		Clinician IF EF	Survey	PM
	Cost	\$	A6	Clinician IF EF beneficiary/patient	Wages, benefits	PM
Outer Setting	Policy	Payment for incentive	A6	CMS Contract	Contract 10/1	PM

Fidelity Measures

Implementation Strategies Data on implementation strategy fidelity (monthly for 12-months) includes readiness assessment (yes/no by manager/clinician), training (#CAPABLE certification), IF/EF (#/type), and audit and feedback (# reports viewed/# actions). Actions coded will include training, coaching, consultation, supervision, modeling, problem solving, and providing feedback, supporting, instructing, demonstrating, and assisting with evaluation.

Acceptability of training by clinicians, IFs, and EFs will be evaluated by number completing training and via conduction of pre-/post- tests devised in our prior work.

Costs of implementation will be estimated based on the time spent in Bb, training, and meetings.

Measure of policy impact will be examined in the waiver contract.

CAPABLE An EHR assessment (OT [baseline assessment]/SW [mood]/RN [medication review], PCSP (presence of desire of beneficiary), and PN (documentation of brainstorming, problem solving, role modeling) review will provide data of use of CAPABLE as a measure of fidelity comparing pre/post CAPABLE.

1.13 DATA COLLECTION, MANAGEMENT, SAFETY, AND STORAGE

This pragmatic, real-world setting study utilizes employees who are either a supervisor (IF), who is a clinician that oversees the provision of care, or a clinician, who conducts usual waiver care and/or CAPABLE. Both supervisors and clinicians have access to the electronic health records of all their beneficiaries at their site.

- Clinicians and IFs have access to beneficiary data where employed.
- IFs have access to which clinicians are trained in CAPABLE.
- EFs will not have access to beneficiary data at a site where they are not employed.
- Clinician, IF, or EF will not have access to study data.

Protected Health Information

For this study we will collect the beneficiary, clinician, and IF names and IF phone number. The names will be used by the PI/PM in the key to assign a study number and will be used to track progression. All data (Excel sheets) will use the study number (not the name). Only the PI/PM have access to the study key. The Research Assistants will call the internal facilitator's using the provided phone number. No other PHI will be collected for the study.

Data Collection and Management

- for this study will include site, clinician, beneficiary, and fidelity data.
1. Site data will be collected from MDHHS (administrative data) at baseline; and clinicians' leadership and readiness from electronic survey in Qualtrics.
 2. Clinician data collection (characteristics, attitude toward evidence-based care, efficacy) will be from an electronic survey in Qualtrics and from the Bb platform (training knowledge and completion).
 3. Beneficiary outcome data (de-identified) will be from CIM (characteristics and outcomes).
 4. Fidelity data on:
 - a. Implementation completion (SIC) will be collected from telephone survey conducted by RAs at the university.
 - b. Implementation strategy use (IF/EF Data Tool) will be collected from telephone survey conducted by RAs at the university.
 - c. CAPABLE will be collected from the PI/PM examination of the EHR (assessment, PCSP, and PNs).

The only study members that will have access to identifiable data are the PI and PM. The PM will assign study numbers and keep a key with site and clinician identifiers, separate from any data Excel sheets, so that all Excel data sheets remain de-identified (no name, address, phone, Medicaid#, etc.).

MDHHS

Per the DUA, MDHHS will provide administrative data via a data transfer to the university (PI/PM). This will occur electronically through a CIM data secure encrypted portal. Data would be downloaded by PI/PM on encrypted jump drives; and stored in a locked file cabinet in GVSU CHS Room 323 (Research Center) with a door that is locked at all times and only accessed by faculty approved to use the room. Only the PI/PM have access to the locked files cabinet.

CIM

Per the DUA, CIM will provide de-identified beneficiary outcome data via a data transfer to the university (PI/PM) at the end of the site's project time period.

- This will occur electronically through a CIM data secure encrypted portal.
- Data would be downloaded by PI/PM on encrypted jump drives; and stored in a locked file cabinet in GVSU CHS Room 323 (Research Center) with a door that is locked at all times and only accessed by faculty approved to use the room.
 - Only the PI/PM have access to the locked files cabinet.
- Data for the study would not be available to the site, clinicians, or supervisors.

Qualtrics

Qualtrics is a web-based survey creation, collection, and analysis software tool that can be used for the creation of open surveys, targeted (panel) surveys, and open polling. Qualtrics provides secure, intuitive, web-based interfaces for users to enter data, and users with approved permissions/passwords can access the system with an Internet connection. Qualtrics servers are hosted in world-class data centers with all the necessary physical security controls (e.g., 24/7 monitoring, cameras, visitor logs, entry requirements.). Qualtrics has Transport Layer Security (TLS) enabled to encrypt respondent traffic. Communications are sent over TLS connections, which protects communications by using both server authentication and data encryption. This ensures that data in transit is safe, secure, and available only to intended recipients. Qualtrics software is available to all university faculty and staff as a site license, centrally funded. Qualtrics survey data is protected, and only available to the survey designers.

- For this project, the PI/PM will construct all electronic and phone surveys in a Qualtrics platform.
 - Surveys were designed so each question on the survey will be voluntary and may be skipped.
 - Only the PI/PM will have access to the Qualtrics platform where surveys will be deployed for this study.
 - Only the PI/PM will have access to the Qualtrics platform identifiable data for this study.
 - RAs conducting the telephone surveys of IFs will complete a survey in Qualtrics.
- After completion of a survey, the data will be downloaded in an Excel format by the PI/PM on encrypted jump drives; and stored in a locked file cabinet in GVSU CHS Room 323 (Research Center) with a door locked at all times and only accessed by faculty approved to use the room.
 - Only the PI/PM have access to the locked files cabinet.
- Data will be de-identified by the PI/PM prior to use of the data by RAs or statistician.
 - De-identified data would be stored on encrypted jump drives; and stored in a locked file cabinet in GVSU CHS Room 323 (Research Center) with a door that is locked at all times and only accessed by faculty approved to use the room.
- Data for the study would not be available to the site, clinicians, or supervisors.

Bb

Blackboard (Bb) is a virtual learning environment and course management system developed by Blackboard Inc. Bb is Web-based server software features course management, customizable open architecture, and scalable design that allows integration with information systems and authentication protocol. For this study, we will deploy clinician (RN/OT/SW) and IF/EF training in Bb.

- The Bb training course's identifiable data will be solely available to designers (PI/PM) and not available to other project or site staff at any time.
- Data collection on clinician (RN/OT/SW) and IF/EF training knowledge (pre/post-test) and completion (finished training) will be collected from Bb by the PI/PM.
- Data from Bb would be downloaded by PI/PM on encrypted jump drives; and stored in a locked file cabinet in GVSU CHS Room 323 (Research Center) with a door that is locked at all times and only accessed by faculty approved to use the room.
 - Only the PI/PM have access to the locked files cabinet.
- Data will be de-identified by the PI/PM prior to use of the data by RAs or statistician.
 - De-identified data would be stored on encrypted jump drives; and stored in a locked file cabinet in GVSU CHS Room 323 (Research Center) with a door that is locked at all times and only accessed by faculty approved to use the room.
- Data for the study would not be available to the site, clinicians, or supervisors.

Month obtained	DATA COLLECTION: Obtained from and What Obtained				
	MDHHS	Clinicians (RN/OT/SW)	IFs	EFs	CIM
0	#beneficiaries #staff #supervisors #years MiChoice CQAR 2015-17	Consent Demographics ILS ORCA	Consent Demographics ILS ORCA	Consent Demographics ILS ORCA	MDS in EHR
1		Consent Demographics EBPAS GSE Train: CAPABLE pre/post/satisfaction	Consent Demographics EBPAS GSE Train: CAPABLE pre/post/satisfaction Train: Facilitation pre/post/satisfaction	Consent Demographics EBPAS GSE Train: CAPABLE pre/post/satisfaction Train: Facilitation pre/post/satisfaction	
2			SIC; IF/EF Data Tool		PSCP & PNs in EHR
3			SIC; IF/EF Data Tool		PSCP & PNs in EHR
4			SIC; IF/EF Data Tool		PSCP & PNs in EHR
5			SIC; IF/EF Data Tool		PSCP & PNs in EHR
6			SIC; IF/EF Data Tool		PSCP & PNs in EHR
7			SIC; IF/EF Data Tool		PSCP & PNs in EHR
8			SIC; IF/EF Data Tool		PSCP & PNs in EHR
9		EBPAS GSE	EBPAS GSE SIC; IF/EF Data Tool	EBPAS GSE	PSCP & PNs in EHR
10			SIC; IF/EF Data Tool		PSCP & PNs in EHR
11			SIC; IF/EF Data Tool		PSCP & PNs in EHR
12	Cost		SIC; IF/EF Data Tool		MDS, PSCP, PNs in EHR
	Policy	Review of CMS Contract			

The above table depicted deployment of data collection activities by month, where the data will be collected from, from whom the data source is (site, clinician, IF, beneficiary), and which measures (characteristics/tool) and tools (SIC, GSE, EBPAS, etc.) are used to collect the data.

Data Security

Data storage and security will be assured as per GVSU policies and placed in secure password-protected platforms and is described in detail in the Data Safety Monitoring Plan (DSMP) and overseen by the Data Safety Monitoring Board (DSMB) as stated in the DSMP Charter.

1.14 DATA ANALYSIS

Preliminary analysis

The distributions of outcomes, mediators, and potential covariates will be assessed, outliers will be investigated by inspecting the residuals, and models described below will be fit with and without outliers to examine their influence on the results. Analyses will be implemented in SAS 9.4 as follows:

Aim A1 To test the effects of MiCAP with IF alone versus MiCAP with IF+EF with respect to the site-level outcomes of adoption and sustainability (**primary**) and beneficiary-level outcomes of ADL/IADLs, pain, depression, falls, emergency department (ED) visits and hospitalizations (**secondary**) over the next 12 months. Primary outcomes will be analyzed using a linear mixed effects model with repeated measures: 11 monthly measures of the SIC, 11 monthly summary records of clinician's actions based on EHR documentation, and monthly for 9 months measures from IF tools (statistical model #1). Covariates will include trial arm, variables used in randomization (site's size and CQAR score), and time entered as a class variable to model potentially non-linear patterns. In addition, we will use general liner model to analyze clinicians' fidelity training data. Log-rank test and Cox proportional hazard modeling will be employed to analyze time spent in each stage (treated as censored if a site does not complete a given implementation stage). The test of significance of the coefficient of the trial arm variable will yield the formal test of hypothesis associated with this aim for the main (time-averaged) effect of IF+EF v. IF alone. The analysis of secondary beneficiary-level outcomes will employ use generalized linear model with appropriately distributed errors and the random effect of site added to account for nesting of individuals within sites. For counts of falls and health service use, Poisson error distribution will be specified. Alternatively, as a zero-inflated Poisson or negative Binomial model based on the distribution of the counts will be fit. The explanatory variables including trial arm will be evaluated as predictors of zero inflation (whether or not the count is zero), and as predictors of the magnitude of the count when it is not zero. Pre-intervention MDS assessment will be used to obtain baseline version of each outcome, which will be included as a covariate to explain the variation in post-intervention outcomes.

Aim A2 Mechanism-of-action To determine whether the effects of EF+IF versus IF on primary outcomes are mediated by clinician attitude or self-efficacy at 9 months. In addition to statistical model #1, statistical model #2 will be fit at the clinician level with site as a random effect to account for nesting of clinicians within sites. To test for mediation, trial arm will be treated as the independent variable; each of the potential mediators (one at a time) will be tested for their effect on the outcome variable. We will use a bias corrected bootstrapping analytic strategy⁸⁶⁻⁸⁷ based on 5000 bootstrap samples to estimate confidence intervals around the indirect effect of the trial arm on the outcome variable, through the mediator. To establish mediation, the 95% confidence interval around the indirect must not include 0.

Aim A3 To benchmark the effects of IF and EF+IF on beneficiary outcomes following implementation as compared to pre-intervention. The analysis of this aim will use 2 repeated measures of beneficiary outcomes: at the start of this study (pre-intervention) and in the following 12 months. Time by trial arm interaction will be included. The least square (LS) means according to the interaction term will be output from this model, and differences from pre-to-post CAPABLE will be evaluated for each arm to gauge the magnitude and practical meaning of improvements.

Exploratory Aim A4 To compare the primary and secondary outcomes within 12 months, potential mediators at 9 months, and baseline leadership and readiness for sites with SIC of $>50\%$ versus sites with $SIC \leq 50\%$ at 6 months in each arm. General or generalized linear models (as appropriate based on outcome or potential mediator distribution) will include the binary indicator of whether SIC at 6 months is $>50\%$ or $<50\%$ in interaction with the trial arm variable. Differences between LS means according to SIC level will be tested within each arm. Because these analyses are exploratory, in addition to formal tests of significance, the effect sizes will be estimated.

Exploratory Aim A5 To explore whether baseline site leadership and readiness moderate the impact of EF+IF compared to IF on primary and secondary outcomes within 12 months in order to determine which sites may

require facilitation that is more intensive. To address this aim, statistical models described under analysis for Aim 1 will be modified to include trial arm by potential moderator interaction. The effect sizes that correspond to the interaction term will be estimated.

Exploratory Aim A6 To evaluate clinician satisfaction at 1 month, and the cost of implementation and policy impact for IF and IF+EF at 12 months. We will use descriptive statistics to summarize clinician satisfaction with training and the cost of implementation. We will use qualitative thematic analysis to analyze all qualitative data on survey tools. We will report on the policy impact as evidenced in the State Contract for the Medicaid Waiver program.

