Dose	Surveys completed Baseline	1-hour discussion weekly	2-hr Bb and 2-hr training; Remediate prn	4-hr online Bb and 4-hr in person training	Meet weekly 1-hour	Weekly for 30 minutes to 1 hour until issues resolved	Weekly results to scorecard in Bb and IF reviews with clinicians; EF reviews with IF
Outcomes affected	Acceptability, readiness	Acceptability	Adoption, sustainability			Adoption, sustainability	Adoption, sustainability, outcomes

Implementation Strategies

Training Clinicians (RNs/OTs/SWs) will be trained in CAPABLE principles, approaches, techniques, and documentation (4-6 hours; pre/post-test).

Interdisciplinary coordination (RNs/OTs/SWs) will be led by IFs, focused on care coordination to promote teamwork; using brainstorming/problem solving care issues to support beneficiary goal attainment.

IFs will **facilitate** and EFs will provide **centralized oversight** for Arm 2 IFs. An IF at each site and an EF (from prior work and were trained and early adopters of CAPABLE) will be selected by the PI and will be trained (2 hours; and take a pre/post-test) in facilitation. IFs will encourage clinicians to complete CAPABLE training; and for those trained, provide feedback; facilitate fidelity to CAPABLE; and conduct remediation as needed from Month 1 through 9. EF will facilitate IF's work with clinicians trained in CAPABLE and assistance will be tailored to a site's needs.

Audit and Feedback on CAPABLE and implementation strategy fidelity data will be provided to IFs to be used to provide feedback to clinicians and develop an improvement plan as needed. The EF will use the data to facilitate IFs and develop an improvement plan as needed.

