1.16 RANDOMIZATION

Randomization for this study occurs at the site level. Sites will be randomized by the PM, to **Arm 1** (MiCAP with IF) or **Arm 2** (MiCAP with IF+EF) using the following steps.

Step 1: Data on site size (number of beneficiaries [patients]) and Clinical Quality Assessment Review (CQAR) scores will be obtained.

Step 2: We will block sites in pairs with similar size and CQAR scores, and flip a coin to determine **Arm 1** or **Arm 2** assignment for study.

The PM will maintain a confidential file documenting study Arm by site. Only the PI/PM will know Arm assignment by site.

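### Aim A1 tests the monthly IF-tool series as a primary adoption outcome, although the tool records delivery of facilitation and external facilitation is what was randomised

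*Combined protocol and SAP*

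**What the plan says.** Section 1.14 (Aim A1) names three monthly series as primary outcomes under statistical model #1: the SIC, summaries of clinician actions in the EHR, and "monthly for 9 months measures from IF tools". It then states: "The test of significance of the coefficient of the trial arm variable will yield the formal test of hypothesis associated with this aim".

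The other sections describe the IF tool as follows:

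- Section 1.12, measures table: the adoption construct includes "Fidelity to IF/EF", measured on IFs and EFs with the IF data tool.
- Section 1.12, fidelity measures: implementation-strategy fidelity covers "training (#CAPABLE certification), IF/EF (#/type), and audit and feedback (# reports viewed/# actions", with actions coded as coaching, consultation, supervision and similar.
- Section 1.13: "Implementation strategy use (IF/EF Data Tool) will be collected from telephone survey conducted by RAs at the university".

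Section 1.16 randomises sites to MiCAP with IF (Arm 1) or MiCAP with IF+EF (Arm 2). Section 1.11 adds that "EFs will provide centralized oversight for Arm 2 IFs", names the IF as the target of the EF, and gives the EF dose as "Weekly for 30 minutes to 1 hour until issues resolved". IFs work in both arms.

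**The concern.** The tool logs the facilitation that took place. EF facilitation is the randomised contrast, and IF behaviour is what the EF is meant to influence. An arm difference on this series would therefore show that more facilitation was delivered. It would not show that sites took up CAPABLE.

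The series has the same primary status as SIC and the EHR actions, and section 1.14 gives no hierarchy or multiplicity rule. A significant arm coefficient on this series alone could be reported as a primary effect on adoption.

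Two later aims inherit the problem because they reuse the primary outcomes. Aim A2 would ask whether clinician attitude or self-efficacy at 9 months mediates the effect of arm on facilitation already logged up to that month, which reverses the intended order. Aim A5 would judge which sites need more intensive facilitation by using facilitation volume as the outcome.

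**Working it through.** **Inputs from the plan.** Section 1.15: 9 sites per arm, correlation 0.7, 11 repeated measures, detectable d of about 1.2. Section 1.14: 9 monthly IF-tool measures. Section 1.11: EF contact weekly at most, starting about 1 month after implementation, with no end date; IF work in months 1 to 9.

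**Assumptions.** Two-sided 0.05 and 80% power, since section 1.15 states neither for the site-level outcomes. SD of a site's monthly contact count from 2 to 6, since the documents give none.

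**1. The plan's own figure.** The SD of a site's time average, in single-month SD units, is √[(1 + (m − 1)ρ)/m].

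- For m = 11: √[(1 + 10 × 0.7)/11] = 0.853. The standard error of the arm difference is 0.853 × √(2/9) = 0.402. A noncentral t with 16 df gives d = 1.200 at 80% power, so the stated 1.2 reproduces.
- For m = 9, as planned for the IF tool: √[(1 + 8 × 0.7)/9] = 0.856, and d = 1.205.

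**2. Ceiling on the built-in difference if EF contacts are scored.** At one contact a week:

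- 9 months × 52/12 = 39 contacts per Arm 2 site.
- With the first month removed for the later EF start, 8 × 52/12 = 34.7, about 35.

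Arm 1 is planned to have none. Both figures are upper bounds, because contact stops once issues are resolved.

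**3. Chance that this alone gives significance for Arm 2.** Suppose IF activity is equal in both arms and EF adds k contacts a month. Then d = k/SD, and the noncentrality is d/(0.856 × √(2/9)) = d/0.404. For k = 4 and SD = 2, d = 2 and the noncentrality is 4.95. The probability of exceeding the upper critical value on 16 df is:

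| EF contacts a month | SD 2 | SD 4 | SD 6 |
|---|---|---|---|
| 4 | 0.996 | 0.64 | 0.34 |
| 2 | 0.64 | 0.21 | 0.12 |
| 1 | 0.21 | 0.08 | 0.06 |
| EF not counted | 0.025 | 0.025 | 0.025 |

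**4. If only IF actions are scored.** The built-in shift is zero, which is the last row. What remains is a question of meaning. Section 1.11 has IFs carry out remediation and draw up improvement plans when the need arises. A struggling site can therefore log more actions than one that took up CAPABLE easily, so the count has no fixed direction as a measure of adoption.

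**5. After removal.** SIC and the EHR actions keep 11 measures, so d stays at 1.20. Counting only the monthly series, each tested at an assumed 0.05 and treated as independent, the chance of at least one false positive falls from 1 − 0.95³ = 0.143 to 1 − 0.95² = 0.0975.

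**The case against.** The strongest defence is that section 1.14 refers to IF tools, not IF/EF tools. The 9 months match the period in which IFs work with clinicians in both arms. The schedule in section 1.13 places the tool in the IF column and leaves the EF column empty for months 2 to 12, apart from the two clinician scales at month 9. Research assistants collect it by telephoning IFs. A score of IF actions only is therefore plausible, and on that reading EF support could change IF behaviour or fail to, which is a genuine randomised contrast. The protocol also lists facilitator fidelity under adoption, and in a Hybrid-3 implementation trial that is a defensible choice of construct.

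Much of this stands. A reader might infer that the arms must differ on the series by construction. The documents support that only for EF items. The tool itself is a listed attachment that is not among the documents, and no scoring rule is given. A reader might also infer that a significant result is nearly certain. That holds only at the most extreme combination in the table.

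The defence does not settle the matter. The schedule and section 1.13 call it the IF/EF tool, the measures table applies the IF data tool to both roles, and nothing excludes EF items. On the IF-only reading the series is still facilitation input that the EF targets, and part of it rises with need.

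**Conclusion.** The concern holds in this form: a record of strategy delivery is tested between arms as a primary adoption outcome.

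How much of the arm difference is built in depends on a scoring rule that the plan does not give. If EF contacts count, the chance of a significant result for Arm 2 with no change in IF activity runs from 0.996 down to 0.06 over the assumed 1 to 4 contacts a month and SD of 2 to 6. If they do not count, it is 0.025 and the objection is one of interpretation only.

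The figure of 39 contacts is a ceiling, not an estimate. Zero EF contact in Arm 1 is also only the plan: the strategy table in section 1.11 mentions moving low adopters between arms without giving the rule, and that would dilute any built-in difference.

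A reader might conclude that the whole primary analysis is compromised. The documents do not support that, because SIC, its time-in-stage analysis and the EHR-documented actions are separate measures.

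**What to change.** In section 1.14, move the IF/EF tool series out of the primary Aim A1 tests, and out of the Aim A2 and A5 analyses that reuse the primary outcomes. Report it by arm as strategy fidelity, with EF and IF actions shown separately. Keep the formal Aim A1 tests on SIC and on EHR-documented CAPABLE actions. At minimum, state the scoring rule and exclude EF contacts from any series tested as primary.

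In the same edit, reconcile the tool's timing. Section 1.12 has strategy fidelity recorded monthly for 12 months, the schedule in section 1.13 shows months 2 to 12 (11 records), and section 1.14 analyses 9 months, although months 2 to 9 yield only 8 records.

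The cost is a change of wording. The same data are collected and reported. The one loss is that a component the protocol lists under adoption becomes descriptive.

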1.18 INFORMED CONSENT AND HIPAA COMPLIANCE

Clinician Informed Consent Clinician (RN/OT/SW/IF) informed consent will be conducted and an electronic signature obtained on the consent form approved by IRB prior to data collection and CAPABLE training. The consent form will be modified and approved by the IRBs, if changes are necessary, prior to use.

Beneficiary Opt-out Consent and HIPAA (Health Insurance Portability and Accountability Act)

Authorization Alteration via a waiver of documentation of informed consent for the Medicaid beneficiaries will occur via two modes.

- For current Waiver beneficiaries: the State or sites will mail the Opt-out Consent document or the sites will hand deliver opt-out consent form to the beneficiary during the next home visit.
- For new Waiver beneficiaries: sites will include Opt-out Consent document in enrollment packets, which will be hand delivered to the beneficiary during their initial home visit in the Mi Choice program.

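### The general linear model for clinicians' training fidelity has no site term; if fitted to individual clinicians and used to compare arms, its test is anti-conservative

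*Combined protocol and SAP*

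**What the plan says.** All references are to the combined protocol and SAP.

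- **Model.** Section 1.14, Aim A1: "In addition, we will use general liner model to analyze clinicians' fidelity training data". Nothing is said about the unit of analysis or about site.
- **Randomisation.** Section 1.16 assigns arms to sites, in pairs matched on size and CQAR score.
- **Measure.** The table in section 1.12 lists "Fidelity to training" under Adoption, for Aims A1 and A2. The clinician is the one measured, and the method is "Type/date/# done". The fidelity text in the same section describes it as "training (#CAPABLE certification".
- **Source.** Section 1.13 says that training knowledge and "completion (finished training) will be collected from Bb by the PI/PM".
- **Other models for individuals.** In the same Aim A1 paragraph, the beneficiary model has a random site effect. For Aim A2, "statistical model #2 will be fit at the clinician level with site as a random effect to account for nesting of clinicians within sites".

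**The concern.** Arm is constant within a site, so the arm contrast varies only between the 18 sites and must be judged against between-site variation. A general linear model fitted to individual clinicians without a site term judges it against residual error that is mostly within-site. If clinicians at the same site resemble each other at all, the standard error is too small and the p-value too favourable.

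Some resemblance is plausible, because each site has its own internal facilitator and section 1.11 says that "IFs will encourage clinicians to complete CAPABLE training; and for those trained, provide feedback".

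The sentence can also be followed in two ways. Two analysts could report different p-values for the same Adoption measure, one from several hundred clinicians and one from 18 sites.

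**Working it through.** **Inputs from the documents**
- 18 sites, 9 per arm (sections 1.5 and 1.15).
- 575 clinicians (section 1.5), so 575/18 = 31.9 per site. This is the largest possible average, because participation is voluntary (section 1.17).
- ICC 0.01, the plan's only ICC, set for beneficiary outcomes (section 1.15).

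**Assumption.** Two-sided 5% level. The plan states no level for Aim A1.

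**Step 1: the plan's own clustering arithmetic.** Design effect = 1 + (m − 1) × ICC. With m = 750 this is 1 + 749 × 0.01 = 8.49. The effective size is 9 × 750 / 8.49 = 795 per arm. The detectable effect at 80% power is (1.96 + 0.84) × √(2/795) = 0.14. All three match section 1.15, so the plan applies this correction to beneficiaries. It gives no corresponding figure for clinicians.

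**Step 2: the same formula for clinicians.** Design effect = 1 + (31.9 − 1) × 0.01 = 1.309.

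**Step 3: true error of an arm test that ignores site.**
- Error = 2 × [1 − Φ(1.96 / √DEFF)].
- 1.96 / √1.309 = 1.713, which gives about 8.7%.
- A check from the mean-square distribution of the unclustered F test with 18 equal sites also gives 8.7%.

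**Step 4: how the figure moves.** Only the first row uses document figures throughout (apart from the 5% level). In the other rows, the cluster size, the share of variance explained or the ICC is assumed.

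| Clinicians per site | ICC | Between-site variance explained by size and CQAR | DEFF | Error |
|---|---|---|---|---|
| 31.9 | 0.01 | none | 1.309 | 8.7% |
| 20 | 0.01 | none | 1.19 | 7.2% |
| 10 | 0.01 | none | 1.09 | 6.0% |
| 32 | 0.01 | half | 1.156 | 6.8% |
| 31.9 | 0.05 | none | 2.55 | 22% |
| 31.9 | 0.10 | none | 4.09 | 33% |
| 32 | 0.05 | half | 1.795 | 14% |
| 32 | 0.10 | half | 2.632 | 23% |

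For the half-explained rows, residual ICC = 0.5 × ICC / (1 − 0.5 × ICC). For ICC 0.01 that is 0.005/0.995 = 0.00503, and DEFF = 1 + 31 × 0.00503 = 1.156.

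At the small end the effect vanishes into noise. With 8 clinicians per site, ICC 0.01 and half explained, the formula gives 5.4%. Simulation of that case (4,000 null runs each) gave 4.8% for a continuous outcome and 5.0% for a binary one, with a Monte Carlo standard error of 0.34 points.

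**Step 5: one value per site.** A general linear model on 18 site values with intercept, arm, size and CQAR leaves 18 − 4 = 14 residual degrees of freedom. Over 36 simulated settings its error averaged 4.95% (range 4.1 to 6.1%), so the nominal level holds.

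**The case against.** **The unit may be the site.** The plan calls adoption a site-level outcome. It describes the training measure in terms that could be site counts, and section 1.15 considers only site-level and beneficiary-level outcomes for Aim 1. It writes in a site effect where it says individuals are the unit, so the absence here might mean that they are not. This stands as an open reading, and on that reading the test is valid. But no text states it. The sentence refers to clinicians' data, the measures table names the clinician, and the site effect in model #2 is written for the Aim A2 mediation analysis, so it does not carry over.

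**The arm comparison is inferred.** The sentence says only that the data will be analysed, and the formal Aim A1 test is described as time-averaged, which fits the repeated-measures model. This stands as a condition on the point. The aim is nevertheless a comparison of arms, and the paragraph attaches its formal test to the arm coefficient.

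**Nothing may vary.** Section 1.7 includes only clinicians trained in CAPABLE. But section 1.18 has "an electronic signature obtained on the consent form approved by IRB prior to data collection and CAPABLE training", and facilitators then encourage completion, so consented clinicians can differ in completion. This is an inference, though a reasonable one.

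**The consequence is small.** Training is scheduled at month 1, while external facilitation starts one month after implementation, so part of the training may precede any difference between arms. That dilutes the contrast but does not correct the error rate. With equal site sizes, ignoring site distorts the standard error and not the estimated difference. It remains true that this is one process measure among several.

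**Conclusion.** The point holds conditionally. As written, the sentence permits a clinician-level model without a site term. If that model is used to compare arms, its error exceeds the nominal level for any positive residual between-site ICC. The figure of about 8.7% is an illustration: it borrows a beneficiary ICC, takes all 575 clinicians, lets size and CQAR explain nothing, and assumes a two-sided 5% level. It is neither a ceiling nor a floor.

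Three stronger readings are tempting, and the documents do not support them:
- *That the plan definitely analyses clinicians without clustering.* The unit is unstated, and a valid site-level analysis is compatible with the text.
- *That errors of 14 to 33% are to be expected.* These rest on assumed ICCs; the documents give none for clinicians. Nor do the documents establish a lower bound above 5%.
- *That the primary analysis is compromised.* The repeated-measures model (#1) is not touched. The effect is confined to training fidelity.

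The sentence should be corrected because the gap concerns a component of a primary construct and is cheap to close.

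**What to change.** Replace the sentence in section 1.14 with one of the following, according to what was intended.

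- **Clinician level:** *Clinician-level training fidelity will be analysed with a (generalized) linear mixed model with a random intercept for site, covariates arm, site size and CQAR, and between-site degrees of freedom.*
- **Site level:** *Training fidelity will be summarised as one value per site (18 values) and analysed by general linear model with arm, site size and CQAR as covariates.*

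Both use covariates that the plan already names, and neither needs new data. If a site-level analysis was intended, only the wording changes. If an unclustered clinician-level model was intended, the cost is that the p-value may become less favourable.
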